4.0 Study Endpoints*

- The primary study endpoint will be the rewarming of frostbitten extremities for 30 minutes at 38°C.
- The secondary study endpoint will be a survey regarding ease of use of this rewarming modality.
- The primary safety endpoint will be patient pain or discomfort that is determined to be unrelated to the discomfort known to be associated with rewarming frostbitten tissue. Two consecutive temperature measurements above 42°C will prompt the cessation of the SVR.

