6.0 Procedures Involved*

- Patients presenting to the ED at Dartmouth-Hitchcock and external study sites with acute frostbite (tissue still frozen) of the hands and/or feet will be identified and approached for recruitment. Patients not entering the study will continue to be treated by ED providers in the traditional fashion.
- Patients recruited for the SVR study will be consented to have their circulating warm water bath(s) heated by the novel SVR method. Providers or nurses caring for the study subjects will be consented to participate and will 1) conduct the SVR procedure, and 2) complete a questionnaire. A researcher will gather SVR equipment and attach two thermometers on the basin: one on the side nearest the SVD, the other on the opposite side. The researcher will verbally walk the provider or nurse carrying out the SVR through the following steps. A 15 L Sterilite® basin will be filled to the marked line (12cm) with water from jugs at room temperature, for each frozen extremity. One extremity can be rewarmed in a single basin, with the possibility for up to four simultaneous SVR basins for a patient with frostbite of all hands and feet. The SVD will be attached to the distal edge of the basin, with one SVD per rewarming basin. The SVD will be turned on and set to maintain the bath at a constant 38°C for 30 minutes duration. The thermometers will be powered on continuously and the researcher will record temperatures simultaneously from each thermometer and the SVD every 2 minutes. At the end of the 30 minute treatment, the extremity will be assessed by the researcher for warmth and pliability. If the extremity still feels cold or frozen, an additional 30 minutes in the water bath will commence, with

PROTOCOL TITLE: Assessment of Sous Vide Water Baths for Acute Rewarming of Frostbitten Extremities.

subsequent reassessment. Rewarming will be considered complete when the affected tissue becomes red or purple, soft, and pliable.

- Patients who do not consent to SVR and elect for traditional water bath management will be asked for their consent to record the similar demographic, water temperature, and time-to rewarm data as in the SVR treatment arm. After re-warming is complete, the provider will be asked to fill out a survey regarding the ease of use and efficacy of the SVR.
- *Describe:*
 - *Procedures performed to lessen the probability or magnitude of risks.*

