PROTOCOL TITLE: Assessment of Sous Vide Water Baths for Acute Rewarming of Frostbitten Extremities.

- Providers assigned to a patient in the emergency department who is determined to have acute frostbite will be targeted.
- The provider's role will be to identify an acute frostbite patient and ask their patient whether they would be interested in hearing more about and potentially participating in a study assessing a new way to rewarm their frostbitten tissue.
- If the patient agrees, the provider access the study on-call investigator list (posted in the ED provider area) and inform a researcher of the patient and need to discuss the stud and potentially enroll the patient.
- *Recruitment:*
 - Providers assigned to a patient in the emergency department who is determined to have acute frostbite.
- *Eligibility:*
 - Any provider managing a frostbite patient at the training levels of PA, APRN, resident physician, fellow, or attending physician are eligible.
- *Consent Process:*
 - Once the patient has consented to participate, the provider will be consented in an area of the emergency department separate from the patient's room, using the provider consent form.
- *Risks/Benefits:*
 - Risks to providers should be minimal. We do not anticipate providers having any difficulty with voluntary decision-making for this study.
 - Benefits to the provider may include improved work flow due to the decreased labor in maintaining a SVR water bath in comparison to manual water bath management. Additionally, participation will provide a firsthand opportunity to treat acute frostbite with a new modality that has potential for increased use in the future.
- *Data Collection:*
 - After successful completion of the SVR, providers will be asked to take a short, 6-question paper survey regarding ease-of-use of the SVR.

PROTOCOL TITLE: Assessment of Sous Vide Water Baths for Acute Rewarming of Frostbitten Extremities.

- Paper data collection forms will be kept in a locked office until transferred by the PI to a Microsoft excel file on a password-protected DH computer.

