17.0 Data Management* and Confidentiality

- *Describe the data analysis plan, including any statistical procedures or power analysis.*
 - The primary outcomes are whether or not the tissue rewarmed and the ability of the SVD to maintain accurate target water temperature. Descriptive statistics will be performed to describe the patient population, time to rewarm, and the provider assessment of ease of use.
- *Describe the steps that will be taken to secure the data (e.g., training, authorization of access, password protection, encryption, physical controls, certificates of confidentiality, and separation of identifiers and data) during storage, use, and transmission.*
 - Paper data collection forms will be kept in a locked office until transferred by the PI to a Microsoft excel file on a password-protected computer. The identifiers and data will be contained in two separate files. Only the PI and sub-investigators will have access to the de-identified data and the PI will retain sole access to the identification key.
 - Data from other sites will be uploaded directly into REDCap database hosted by DHMC to ensure secure data transfer for multicenter analysis. Access to the data on the

PROTOCOL TITLE: Assessment of Sous Vide Water Baths for Acute Rewarming of Frostbitten Extremities.

REDCap database will be restricted to the PI and DHMC study staff.

- *Summarize the record retention plan applicable to the study (taking into account any applicable Dartmouth Department, Division or Research Center requirements, or applicable funding sponsor requirements.)*
 - Records will be stored on-site on the PI's password protected computer for 3 years after publication.
 - *Describe any procedures that will be used for quality control of collected data.*
 - Dual thermometers will act as redundant sampling of water bath temperatures
 - *Describe how data or specimens will be handled study-wide:*
 - *What information will be included in that data or associated with the specimens?*
 - The data collection form will include the MRN of the patient and a numeral used to de-identify the data in the excel file. The collection form will contain a table of recorded water temperatures, including a temperature from each of the two thermometers as well as the SVD every 2 minutes during the rewarming period. Any adverse events will also be recorded.
 - *Where and how data or specimens will be stored?*

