 - Data collection forms filled out by clinicians or investigators will be stored in a locked office until the data is transferred to a Microsoft excel file. The data file will be stored on the password-protected computer of the PI.
 - *How long the data or specimens will be stored?*
 - Data will be stored throughout the duration of the study and manuscript preparation.
 - *Who will have access to the data or specimens?*
 - The data collection forms will be accessible to the clinician filling it out. Once transferred to excel format, only the PI and sub-investigators will have access to the de-identified data. Only the PI and key study personnel will have access to the de-identification number key.

PROTOCOL TITLE: Assessment of Sous Vide Water Baths for Acute Rewarming of Frostbitten Extremities.

- *Who is responsible for receipt or transmission of the data or specimens?*
 - Data collection forms will be deposited in the locked office by the clinician or investigator filling out the form during active rewarming of a subject.
 - Data will be entered into REDCap for further analysis.
 - External sites will enter their data directly into the DH REDCap Database
- *How data or specimens will be transported?*
 - Data will remain on the password protected hard drive of the PI.
 - Deidentified data may be analyzed by additional research team members.

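### Ease-of-use ratings go from identifiable raters to the team that helped them, with no confidential route in the main text, so the secondary endpoint may lean favourable

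*Combined protocol and SAP*

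**What the plan says.** Section 4.0 defines the endpoint: "The secondary study endpoint will be a survey regarding ease of use of this rewarming modality". Section 2.0 lists a favourable verdict on ease of use among the study's hypotheses, and section 17.0 plans descriptive statistics for it.

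- **Who rates.** Section 6.0 states: "Providers or nurses caring for the study subjects will be consented to participate". Under Provider Participation, those "at the training levels of PA, APRN, resident physician, fellow, or attending physician are eligible".
- **What happens before the rating.** Section 6.0: "The researcher will verbally walk the provider or nurse carrying out the SVR through the following steps". Section 10.0 has the PI or a sub-investigator on call to come in, enrol the patient and help with the treatment. Under section 21.0 the researcher also obtains the provider's consent.
- **How the answer is collected.** Providers complete a paper form: "providers will be asked to take a short, 6-question paper survey regarding ease-of-use of the SVR". The next item reads: "Paper data collection forms will be kept in a locked office until transferred by the PI to a Microsoft excel file".
- **Other sites.** Section 17.0: "External sites will enter their data directly into the DH REDCap Database". Access to the data on the "REDCap database will be restricted to the PI and DHMC study staff".
- **Review.** Section 18.0 has the local PI review data after each subject, and the lead site check all entered data for completeness.

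**The concern.** The question is how the answer reaches the study, as distinct from who may rate or how much help they had. A rater who has just been helped by colleagues, and whose answer those colleagues can trace, has a reason to be kind. The investigators expect a favourable result, so any such shift runs in the direction of their hypothesis. A descriptive summary cannot detect or remove it, and it cannot be repaired once the forms are in. What is at stake is the meaning of the secondary endpoint: a high ease-of-use score could partly reflect courtesy.

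**Working it through.** The plan states no power, error rate or success threshold for the survey, and section 12.0 says no sample size was calculated. There is no plan figure to reproduce. The check is a comparison of sections plus some simple arithmetic.

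**1. Is the rater known to the team?** Yes. The researcher consents the provider (21.0) and coaches the procedure (6.0), and an investigator assists (10.0). With 1-5 patients per site (9.0, 12.0), a form linked to a case points to its author whether or not it carries a name.

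**2. Who can see the rating?** At the lead site, the sentence on transfer by the PI directly follows the survey item, so it most naturally covers the survey. At external sites entry is local, and section 17.0 does not say by whom. The PI can read the pooled database in either case.

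**3. Is there a safeguard?** The de-identification in sections 7.0 and 17.0 and the privacy provisions in 19.0 concern patients. The main text gives no unnamed return, independent collection or independent entry for provider ratings.

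**4. How far does transfer by the PI reach?** Inputs from section 1.0: 1-5 patients at the lead site and 5-10 further sites with similar goals. Assumption: one survey per patient.

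Lead-site share = lead-site patients / all patients.

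| Case | Calculation | Share |
|---|---|---|
| Equal enrolment, 10 other sites | 1/(1 + 10) | 9% |
| Equal enrolment, 5 other sites | 1/(1 + 5) | 17% |
| Lowest within the ranges | 1/(1 + 10×5) | 2% |
| Highest within the ranges | 5/(5 + 5×1) | 50% |
| Only the lead site enrols | – | 100% |

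Transfer by the PI would usually touch a minority of ratings. Traceability and the PI's database access apply to all of them.

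**5. How sensitive is the summary?** Suppose two answers cross from not easy to easy. The number two is arbitrary.

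- Section 2.0 range, 5-20 cases: 2/5 = 40 points; 2/20 = 10 points.
- Section 1.0 range, from 1 + 5×1 = 6 to 11×5 = 55 patients: 2/6 = 33 points; 2/55 = 4 points.

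These figures show leverage only. The response scale is not given. The number of surveys is also uncertain: section 6.0 asks for one after successful treatment in one place, and for all acute frostbite patients, consenting or not, in another. If a fixed fraction of raters shifted, the bias would not shrink as numbers grew.

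**The case against.** The case against has several sound parts.

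- A reader might infer that the PI personally reads and types in every rating. The documents do not support that. The sentence concerns paper forms moved to a lead-site computer, and external sites enter their own data. Even at the lead site it is an inference, because section 6.0 names surveys and data collection forms separately and section 17.0 describes the collection form without survey items.
- A reader might also infer that trainees are rating their supervisors' project. Only residents and fellows are trainees. Attendings, PAs and APRNs are eligible and nurses may take part, and no section says that the helper supervises the rater. Courtesy needs no hierarchy, but the hierarchy argument covers only part of the group.
- The survey is described as attached and the provider consent form is a separate document. Neither was available, so it cannot be checked whether a name is asked for or confidentiality promised. Nor does any section say that a researcher is present while the form is completed.
- This is a feasibility study with a descriptive secondary endpoint and no test, so a stated limitation would deal with part of the problem.

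All four narrow the point. None removes it: the rater is known, the rating is visible to people who expect a good result, and the text we have offers no confidential route.

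**Conclusion.** The concern holds in a limited form. Ease-of-use ratings come from identifiable people who have just been helped by the study team, and they go back to that team by a route with no stated confidentiality. They may lean towards the section 2.0 hypothesis. The direction is a reasonable inference; the size cannot be estimated from the documents, and the 40-to-10-point figures must not be read as an expected bias.

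This rests on two assumptions: that the unseen survey and provider consent form contain no safeguard, and that each case has one or few raters. It affects interpretation of a descriptive secondary endpoint only. It touches no error rate or sample size, and neither primary outcome (rewarming and water temperature). It is worth acting on because the remedy is cheap and cannot be applied afterwards.

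**What to change.** 1. In section 6.0, Provider Participation, replace the paper survey with one that the provider completes alone and without a name, directly in the REDCap database already in use. Record the rater's role, and link to the case by study number only.
2. In section 17.0, amend the access wording so that individual ratings are visible only to DHMC data staff, and not to the PI or local investigators until pooled. The same data staff carry out the section 18.0 completeness check for the survey.
3. State this on the provider consent form.
4. Report assisted use and residual identifiability as limitations. A study number at a site with 1-5 patients can still point to a person, so withholding individual answers until pooling does more than removing the name.

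**Cost:** one REDCap form, a change to the access setting and its wording, and a line on the consent form. Missing surveys will be harder to chase.

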7.0 Data and Specimen Banking*

- There will be no specimens banked for future use.
- Individual patient data from the emergency department visit will exist in the patient's EMR.
- A de-identified, numerically listed spreadsheet of the study participants will be stored on the protected Dartmouth-Hitchcock H: drive of the PI. The participant key will exist on the same drive. The PI computer is a D-H managed ThinkPad and will remain on-campus in a locked office shared by the PI.
- Consented subjects will be tracked in the DHH CTMS, OnCore

8.0 Sharing of Results with Subjects*

- Neither the individual subject or study results will be shared directly with the subjects or others, including the subject's primary physician. The study results will be shared via publication.

9.0 Study Timelines*

- *Describe:*
 - Each participant will be enrolled during the study period for this treatment, which includes the emergency department visit. The actual estimated treatment duration is 30 minutes. Some participants may exceed this and be treated for 60-90 minutes.
 - Given the incidence of frostbite and census of the Dartmouth-Hitchcock emergency department, and the requirement for the participant to have acute frostbite (currently frozen) rather than already thawed, it is expected to take the entire cold frostbite season to enroll 1-5 participants per study enrollment location.
 - The estimated date for the investigators to complete this study: Sept 11, 2023.

PROTOCOL TITLE: Assessment of Sous Vide Water Baths for Acute Rewarming of Frostbitten Extremities.

10.0 Inclusion and Exclusion Criteria*

- The primary and sub-investigators will identify patients presenting to the emergency department with a chief complaint of frostbite, as seen on the EMR patient tracking board. Reminder signs and group awareness in the emergency department of this study will help alert providers of the potential to approach subjects for enrollment who presented to the department with an associated complaint, such as “foot pain” or other chief complaint, but determined to have acute frostbite on initial examination. The PI or a Sub-I will be on-call to drive to the ED to enroll and consent the patient with the standard forms, and assist with the treatment. Consent will always be obtained in-person, by a study team member with consenting privileges.
Inclusion criteria: Age 18 or up or <17 with parent or guardian able to provide consent, ability to understand English and provide consent to the study, acute frostbite (frozen tissue) of the hands or feet.
- *Exclusion criteria:* Children under age 18 without parent or guardian, frostbite that has already thawed, frostbite (thawed or acute) of tissue other than hands or feet, inability to understand English and to provide consent.
- *Indicate specifically whether you will include or exclude each of the following special populations: (You may not include members of the above populations as subjects in your research unless you indicate this in your inclusion criteria.)*
 - *Adults unable to consent* - Exclude
 - *Individuals who are not yet adults (infants, children, teenagers)* - Include
 - *Pregnant women* - Include
- *Prisoners* - Exclude

11.0 Vulnerable Populations*

- This study presents no more than minimal risk to enrollees. There is no expected increase in risk to children or pregnant women over standard care treatment options. Excluding these populations may limit the sample size of the study.

12.0 Local Number of Subjects

PROTOCOL TITLE: Assessment of Sous Vide Water Baths for Acute Rewarming of Frostbitten Extremities.

- The maximum available to enroll will be enrolled during the study period. The investigators estimate 1-5 patients per study location may be feasible during the cold season.

Describe the statistical methods for determining the sample size for the study

- N/A. As a feasibility study to the use of SVR for acute frostbite, there are no sample size calculations. All potential participants will be approached for enrollment.

13.0 Recruitment Methods

- Patients presenting with acute frostbite in the Dartmouth-Hitchcock Emergency Department and participating centers and whom have expressed interest in participating in the study to their care team will be approached for recruitment during their emergency department visit.
- Patients will be identified by the PI, Sub-Is, and other providers by the chief complaint, which may state frostbite, cold-injury, or pain in an extremity. Word-of-mouth and departmental awareness of this study will assist providers in identifying the appropriateness of recruiting patients that had varying other chief complaints, but found to have acute frostbite on evaluation.
- Subjects will be recruited in person, during their emergency department visit and will be consented by the research team.
- There will be no payments for participation in this study.
- Some participating sites will request a Partial HIPAA Waiver of Authorization for Recruitment Purposes so that the research team can scan the emergency department electronic medical records board for patients presenting with frostbite. It is critical that the SVR is implemented quickly, which allows for the best treatment efficacy. By scanning the emergency department board, the research staff will more rapidly identify frostbite patients and circumvent possible delays in enrollment and treatment.

14.0 Withdrawal of Subjects*

- Subjects will be withdrawn without their consent for safety reasons or medical necessity. Criteria as follows: If water bath temperatures are recorded at over 42°C on two consecutive readings during the

PROTOCOL TITLE: Assessment of Sous Vide Water Baths for Acute Rewarming of Frostbitten Extremities.

same treatment phase, if subject is judged by the treating clinician to have pain greater than expected for frostbite rewarming, or if a separate medical issue arises in the subject in which urgent treatment necessitates termination of the research.

- *Describe any procedures for orderly termination.*
 - The SVD will be powered off and the water bath maintained manually by medical staff.
- *Describe procedures that will be followed when subjects withdraw from the research, including partial withdrawal from procedures with continued data collection.*
 - Withdrawal from the research will preclude any further data collection. Data already collected at the time of the withdrawal will be analyzed with other study data but noted that the study terminated prematurely.

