 - The blood pressure cuff used in the standard emergency department assessment of vital signs will be placed on an extremity that is not currently being rewarmed, whenever possible, to avoid constricting blood flow to the affected tissue.
- *Data Collection:*
 - Prior to rewarming, physical examination of the patient, including the frozen extremity, will be completed and documented in the EPIC/EMR chart by the provider.
 - Two thermometers, placed in the rewarming basin, will continuously monitor the water temperature. The temperature reading on both thermometers as well as the SVD will be recorded on a paper data sheet by a trained provider at 2-minute intervals until the 30 minutes of treatment are complete.

PROTOCOL TITLE: Assessment of Sous Vide Water Baths for Acute Rewarming of Frostbitten Extremities.

- The researcher will repeat an exam, assessing all extremities being treated by SVR, at 30 minutes to determine warmth and pliability of the tissue, confirming thaw. Rewarming will be considered complete if the affected tissue becomes red or purple, soft, and pliable. The same rewarming criteria applies for all extremities.
 - The provider will be asked to fill out a survey on all acute frostbite patients whom consent to the study protocol, as well as those that do not.
 - *The source records that will be used to collect data about subjects. (Attach all surveys, scripts, and data collection forms.) If there are plans for long-term follow-up (once all research related procedures are complete), what data will be collected during this period.*
 - The patient's age and sex will be recorded. The physical examination and pertinent medical information will be reviewed to confirm the location and extent of the frostbite and for contributing conditions.
 - Demographics and relevant medical history will be accessed.
 - Please see attached surveys and data collection forms.
 - Enrolled subjects may be contacted via phone and myDH or local electronic medical record communication at 6 months post-enrollment to assess long term outcomes of their frostbite. Chart review to assess related complications will also occur at this time.
 - *Explain if any part of this study involves genetic analysis of biological specimens. If yes, explain whether the study is based on one the following:*
 - This study does not involve genetic analysis of biological specimens.

Provider Participation:

- *Role/Activities:*

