18.0 Provisions to Monitor the Data to Ensure the Safety of Subjects*

- *Describe:*
 - *The plan to periodically evaluate the data collected regarding both harms and benefits to determine whether subjects remain safe. The plan might include establishing a data monitoring committee and a plan for reporting data monitoring committee findings to the IRB and the sponsor.*
 - The data will be reviewed by the local PI each time a subject participates in the study, to confirm standard process and to assess for reported adverse events.
 - As the lead site, we will review all data entered into the database for completeness.
 - *What data are reviewed, including safety data, untoward events, and efficacy data.*
 - Signed informed consent, temperature recordings, water bath treatment time required to achieve rewarming, and adverse events will be reviewed.
 - *How the safety information will be collected (e.g., with case report forms, at study visits, by telephone calls with participants).*
 - Adverse events will be recorded on the data collection form during the treatment of the subject in the emergency department.

PROTOCOL TITLE: Assessment of Sous Vide Water Baths for Acute Rewarming of Frostbitten Extremities.

- Adverse events across all sites will be reviewed at a monthly meeting of collaborating sites.
- *The frequency of data collection, including when safety data collection starts.*
 - Data collection will commence when the subject is treated in the emergency department. Data will be reviewed for safety issues after each subject.
- *Who will review the data.*
 - The PI will review the safety data.
- *The frequency or periodicity of review of cumulative data.*
 - The PI will review cumulative data after each subject.
- *The statistical tests for analyzing the safety data to determine whether harm is occurring.*
 - With an expected subject size of 1-5 study participants in each study location, safety data will be reviewed after each subject participates. There will be no need to make estimations.
- *Any conditions that trigger an immediate suspension of the research.*
 - If 1 or more unanticipated adverse events are considered possibly attributable to the use of the SVD, the study will be put on hold pending review of the incident.
- *Describe the procedures for unblinding study therapy on a subject, including documentation of this in the subject's source document.*

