19.0 Provisions to Protect the Privacy Interests of Subjects

- *Describe the steps that will be taken to protect subjects' privacy interests. "Privacy interest" refers to a person's desire to place limits on whom they interact or whom they provide personal information.*

PROTOCOL TITLE: Assessment of Sous Vide Water Baths for Acute Rewarming of Frostbitten Extremities.

- Patients who may meet the enrollment criteria will be approached and asked if they are willing to learn about a research study taking place that they may qualify for. If the patient is not interested they will receive the current standard of care treatment.
- *Describe what steps you will take to make the subjects feel at ease with the research situation in terms of the questions being asked and the procedures being performed. “At ease” does not refer to physical discomfort, but the sense of intrusiveness a subject might experience in response to questions, examinations, and procedures.*
- Potential subjects will have the traditional method of rewarming explained as well as an explanation of how SVR works. They will be informed that research is voluntary and they can withdraw at any point.
- *Indicate how the research team is permitted to access any sources of information about the subjects.*
- The study team will be permitted to access the emergency department chart of the consented subjects to be able to record de-identified sex, age, frostbite location, further information about the case or any adverse event, and patient outcomes. The subject provides consent for this access as part of the informed consent process.

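### Section 14.0 classes over-temperature and excess-pain stops as withdrawals and, read as written, ends data collection on them; the scoring of stopped cases and the survey rule also need one reading

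*Combined protocol and SAP*

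**What the plan says.** **Withdrawal (Section 14.0).** The section opens: "Subjects will be withdrawn without their consent for safety reasons or medical necessity". It names three criteria: two consecutive bath readings over 42°C, excess pain ("if subject is judged by the treating clinician to have pain greater than expected for frostbite rewarming"), and a separate urgent medical problem. A later template prompt asks what happens when subjects withdraw, "including partial withdrawal from procedures with continued data collection". The answer is "Withdrawal from the research will preclude any further data collection", followed by "Data already collected at the time of the withdrawal will be analyzed with other study data but noted that the study terminated prematurely".

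**The same events elsewhere.** Sections 4.0 and 6.0 describe the over-temperature and pain events as ending SVR or the treatment. Standard rewarming follows if the tissue has not yet thawed. Neither section calls this withdrawal. Section 15.0 adds under-heating stops (target not reached in 30 minutes, or below 37°C for more than 5 minutes), which Section 14.0 does not list.

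**Later data.** Section 6.0 makes 6-month contact of enrolled subjects optional, but on the records it is firm: "Chart review to assess related complications will also occur at this time". Section 18.0 has adverse events recorded during treatment in the emergency department (ED) and adds: "Adverse events across all sites will be reviewed at a monthly meeting of collaborating sites". Section 19.0 permits access to the charts of consented subjects for "further information about the case or any adverse event, and patient outcomes".

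**Outcome and survey.** Section 17.0 gives tissue rewarming as one of two primary outcomes, analysed descriptively, with no denominator or unit. Section 4.0 words the endpoint as rewarming for 30 minutes at 38°C. Section 6.0 allows up to four basins per patient. For the provider survey, Section 6.0 (Provider Participation) requires that SVR was completed successfully. Section 1.0 has no such condition, Section 6.0 (Data Collection) covers consenting and non-consenting patients alike, and the procedure description in Section 6.0 places the survey after rewarming is finished.

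**The concern.** The patients caught by Section 14.0 are those whose bath ran too hot or whose pain went beyond what rewarming explains. The device is not FDA approved for medical use (Section 6.0), hot water burns are a listed hazard (Section 15.0), and the pain criterion lies close to the primary safety endpoint in Section 4.0. These are the patients in whom a later complication would say most about the device.

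The plan also contains an odd contrast. Patients who decline SVR are asked to let their time to rewarm be recorded (Section 6.0). A patient who accepted SVR and was stopped for overheating would have recording ended without having asked for it.

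Two smaller gaps follow from the same events. A thaw finished by manual rewarming could be counted towards the primary outcome, because Section 17.0 asks only whether the tissue rewarmed. And a site that follows the Provider Participation text would leave failed attempts out of the ease-of-use endpoint.

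**Working it through.** **1. The passages side by side, for a patient stopped for over-temperature or excess pain who has not revoked consent**

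| Item | Section 14.0 as written | Other text |
|---|---|---|
| Status | Withdrawn from the research | Treatment ended (4.0, 6.0) |
| Data up to the stop | Kept, analysed, flagged | No conflict |
| Thaw status after the stop | Not collected | Not addressed |
| 6-month chart review | Not collected | Will take place (6.0): direct conflict |
| Adverse events after the stop | Not collected | Reviewed across sites, but recorded during ED treatment (18.0): softer tension |
| Chart access | Not used further | Permitted, not required (19.0): softer tension |

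The temperatures or pain that triggered the stop precede it and are kept. The loss is confined to what comes later.

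**2. How often this could arise.** There is no sample size calculation to reproduce (Section 12.0), and no stop rate is given. Under assumed rates, with patients independent, the chance of at least one stop is 1 − (1 − p)^n:

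| Assumed stop rate p | n = 5 | n = 20 |
|---|---|---|
| 5% | 23% | 64% |
| 10% | 41% | 88% |
| 20% | 67% | 99% |

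The values of n are the ends of the 5–20 cases in Section 2.0.

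**3. Effect of one stopped case, counted by patient.** Let n patients start SVR, one be stopped before thaw, and x of the other n − 1 rewarm.

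- Stop counted as not rewarmed by SVR: x/n.
- Stop omitted: x/(n − 1). The difference is x/(n(n − 1)), at most 1/n, reached when x = n − 1.
- Manual thaw credited to SVR: (x + 1)/n. The difference is exactly 1/n.

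So the bound is 1/n: 1/5 = 20.0 points and 1/20 = 5.0 points. With n = 5 and all others rewarmed, the result is 4/5 = 80% if the stop counts as not rewarmed, against 4/4 or 5/5 = 100% otherwise. With n = 20 it is 19/20 = 95% against 100%.

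The site counts in Section 1.0 imply (1 + 5) × 1 = 6 to (1 + 10) × 5 = 55 patients, for which 1/n runs from 16.7 to 1.8 points.

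**4. Counted by extremity.** Assume the stopped patient has k basins that all stop and every other patient has one. The total is N = n − 1 + k and the bound is k/N.

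| | n = 5 | n = 20 |
|---|---|---|
| k = 1 | 1/5 = 20.0 points | 1/20 = 5.0 points |
| k = 4 | 4/8 = 50.0 points | 4/23 = 17.4 points |

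At k = 1 the two units give the same bound. The larger figures need the four-basin patient.

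**The case against.** **Intent.** The strongest reply is that Section 14.0 gives separate answers to separate prompts, and the bar stands only under the prompt about subjects who withdraw. With Sections 4.0 and 6.0 speaking of ending treatment, voluntary withdrawal may be all that was meant. That is plausible. But the sentence carries no such limit, the section opens with involuntary withdrawal, and further sites, still to be named in Section 23.0, will work from the text. The objection makes this a clarification of wording; it does not remove the need for one.

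**Readings that go too far.** Four stronger inferences are tempting, and the documents do not support them.

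- *That stopped cases vanish from the analysis.* Section 14.0 keeps and flags what was collected before the stop, and Section 18.0 has the investigator review the data after each subject.
- *That Section 14.0 alone keeps late injuries from the monthly review.* Section 18.0 ties the adverse event form to ED treatment for every subject, completers included. The firm conflict is with the chart review in Section 6.0.
- *That a stop in one basin withdraws all of a patient's basins.* Withdrawal is worded by subject, but orderly termination speaks of a single device and bath, and each basin has its own device. The text leaves this open.
- *That every stop is a rewarming failure.* Section 6.0 allows for a stop before thaw, which implies that some stops may come after it. Scoring all stops as failures would miscode tissue already soft and pliable.

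**Scale.** This is a small descriptive feasibility study, so the missing unit on its own is a missing detail. The survey conflict is also small: the Provider Participation sentence may have been meant to fix timing. Whether a stop-reason field or a consent sentence already exists cannot be judged, because the attached forms were not available.

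**Conclusion.** The point holds as a contradiction to be reconciled. As written, Section 14.0 ends data collection on patients stopped for over-temperature or excess pain who have not revoked consent, against the planned chart review of complications in Section 6.0. What would be lost is thaw status after the stop and later complications. It should be fixed, with medium confidence, because the authors' intent is uncertain.

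The expected size cannot be stated, since no stop rate is given. By patient, one stopped case moves the rewarming proportion by at most 20.0 points at n = 5 and 5.0 at n = 20. Shifts of 50.0 and 17.4 points arise only if the stopped patient has four basins that all stop and every other patient has one; they should not be quoted as the typical effect. The scoring and survey gaps are secondary.

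**What to change.** 1. **Section 14.0.** Separate *SVR stopped* from *consent to data collection withdrawn*. After an SVR stop, including the under-heating stops in Section 15.0, keep recording rewarming status and adverse events and carry out the 6-month review, unless the patient withdraws consent to data collection. Say whether a stop in one basin applies to the patient's other basins.
2. **Section 17.0.** Report SVR rewarming over all SVR starts and state the unit, patient or extremity. Score each extremity by its status when SVR stopped. Do not credit to SVR a thaw completed by manual rewarming. List stops by reason.
3. **Survey.** Reconcile the Provider Participation text in Section 6.0 with Section 1.0 and the rest of Section 6.0, so that the ease-of-use survey covers every SVR attempt, including failed ones.

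The cost is wording in Sections 6.0, 14.0 and 17.0, a sentence in the consent form if it lacks one, and a few data fields such as stop reason and rewarming status after the stop. No patients are added. Reported rewarming and ease-of-use results may be less favourable. The clinical stopping rules are not changed.
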